2.4. Framework

A superiority hypothesis testing framework will be used. In the main analyses, we will compare whether TRE plus exercise interventions (TRE + Exercise group) is superior to TRE or Exercise alone or the UC (Mediterranean education program only).

2.5. Statistical interim analyses and stopping guidance

No pre-specified interim analyses will be performed, and therefore, a stopping guidance will not be applicable.

2.6. Timing of the final analyses

The final analyses will be performed after the finalization of the data collection and processing of the primary and secondary outcomes.

2.7. Timing of outcome assessment

The primary (i.e., hepatic fat content) and secondary outcomes (i.e., other specific fat depots measured by magnetic resonance imaging [MRI], and cardiometabolic health markers) will be assessed at baseline, post intervention (12 weeks), and at a 12-month follow-up (12 months post intervention). The time frame of each outcome is explained in section ‘5.1 Outcome definitions’

3. Statistical principles

3.1. Confidence and P values

All statistical tests will be two-tailed. *P* for significance will be set at 0.05 and 95% confidence intervals will be estimated. No adjustment for multiplicity will be made as multiplicity adjustments may be of lesser importance in the case of distinct treatment arms.³ Moreover, only one primary outcome will be defined and other outcomes (i.e., secondary outcomes, and exploratory analyses) will not require adjustment for multiple testing. However, we will include a hierarchical analytic approach for the interventions tested and the primary outcome.

3.2. Adherence, attendance, and protocol deviations

During the 12-week intervention period, participants will be required to record their eating times (i.e., exact times of the beginning of the first meal and of the end of the last meal) in a mobile phone app specifically designed for the study. These data will be revised from 2 to 3 times every week, asking the participant for missing records, and will provide insights into their adherence to the prescribed eating window. For participants in the TRE + Exercise group and TRE alone group, each day will be labeled as adherent if the participant meets their self-selected 8-hour (± 30 minutes) eating window. Adherence will then be defined as the percentage of days on which the eating window was met. Finally, we will assess the long-term adherence to the intervention (at the 12-month follow-up). This will allow us to evaluate the sustainability of participants' adherence over an extended period.

Attendance will be defined as percentage of exercise sessions attended by the participant (TRE + Exercise and Exercise alone groups), recorded by the trainers, divided by the actual number of exercise sessions offered (12 weeks x 2 sessions / week = 24).

All protocol deviations made to the protocol (e.g., change in pre-defined inclusion/exclusion criteria, baseline and post assessments, data cleaning/processing) will be reported and described.

3.3. Analysis populations

We plan to use an intention-to-treat approach for our primary analyses, which will include all randomized participants. With this approach, participants are analysed in the groups to which they were originally assigned, regardless of whether they completed the intervention. As a result, some participants will have valid data at both time points, while others may have missing data at baseline, post-intervention, or the 12-month follow-up assessment.

4. Trial population

4.1. Screening data

Screening data will be based on patients who are defined as eligible by the clinical and research team. Screening is performed in three phases:

- 1) Screening based on phone call by the research team.
- 2) Screening based on the eligibility criteria (see '4.2 Eligibility') by the clinicians of the research team.
- 3) Screening during the 2-week lead-in period prior to pre-intervention assessments and group allocation.

More details on the eligibility criteria are provided in '4.2 Eligibility'. The number of patients within each phase will be reported.

4.2. Eligibility

Eligible patients were defined by the inclusion and exclusion criteria. In general, adults with obesity between 25 and 65 years old (both included) who are physically inactive will be included. Specific inclusion and exclusion criteria are:

Inclusion criteria:

1. Aged 25-65 years.
2. Body mass index (BMI) between 30 and $<40 \text{ kg/m}^2$.
3. Weight stability (within 3% of screening weight) for >2 months prior to study entry.
4. Habitual eating window ≥ 11 hours.

Exclusion criteria:

1. History of a major adverse cardiovascular event (e.g., acute myocardial infarction, ischemic or hemorrhagic stroke, or peripheral arterial ischemia, among others), kidney failure, chronic liver disease, or human immunodeficiency virus (HIV) / acquired immunodeficiency syndrome (AIDS).
2. Active endocrinological disease, innate errors of metabolism, myopathies or epilepsy.
3. Patients who have undergone bariatric surgery or other surgical techniques or used for the treatment of other pathologies (e.g., "Roux-en-Y").
4. Rheumatoid arthritis, Parkinson's disease, active cancer treatment in the past year or another medical condition in which fasting is contraindicated.
5. Use of medications that may affect the results of the study such as drugs for glycemic control (e.g., antidiabetic, steroids, beta-blockers, antibiotics, prebiotics, probiotics and symbiotics).
6. Diagnosis of major sleep or eating disorders.
7. Caregiver for a dependent requiring frequent nocturnal care/sleep interruption or shift workers with nocturnal hours.
8. Metal or electrical prosthesis.
9. Foreign bodies in the eyes.
10. Fear of needles and claustrophobia to MRI.
11. Active tobacco or illicit drug use or a history of alcohol abuse treatment (i.e., moderate or severe alcoholism).
12. Participating in a weight loss or a supervised exercise program (i.e., $> 30 \text{ min}$ in 3 times per week, or $> 45 \text{ min}$ in 2 or more times per week at moderate-to-vigorous intensity).
13. Pregnancy and lactation or planned pregnancy (within the study period).
14. Frequent travel over time zones during the study period.

15. Being unable to understand and accept the instructions or the study objectives and protocol.
16. Not having or being able to use a smartphone with Apple iOS or Android OS.
17. Are deemed unsuitable by the investigator for any other reason.

4.3. Recruitment

Information necessary for the CONSORT flow diagram will be collected⁴. For the enrolment phase, we will note the number of patients that are assessed for eligibility by the research team, the number of excluded patients (plus reason for exclusion), and the number of randomized participants. For the allocation, the number of participants allocated to the intervention, and the number of participants who received or did not receive the intervention (plus reasons) will be noted. For follow-up, the number of participants lost to follow-up and the number who discontinued the intervention (plus reasons) will be counted. Finally, the number of participants included in the analyses using the intention-to-treat will be described.

4.4. Withdrawal/follow-up

The number, timing, and reasons (e.g., adverse events, lost motivation to continue with the study, withdrew consent, could not or did not want to attend the post-intervention evaluations) for withdrawal will be noted and described.

4.5. Baseline patient characteristics

A baseline table will be created to describe the characteristics of the study population. The characteristics include general sociodemographic outcomes (e.g., age or sex), anthropometry and body composition (e.g., body weight, height, BMI, waist circumference, fat-free mass, fat mass), cardiometabolic health (e.g., blood pressure, glucose homeostasis, blood lipid profile, liver health markers), dietary intake (e.g., energy intake, percentage of macronutrients) and physical fitness (e.g., cardiorespiratory fitness, muscular strength). The characteristics of the total study population and each study arm will be summarized using mean (SD) or median (interquartile range) for normally and not normally distributed continuous variables, respectively, and as number (percentage) for categorical variables.

5. Analysis

5.1. Outcome definitions

Primary outcome

1. Change in hepatic fat content (baseline and 12 weeks). The quantification of hepatic fat content will be performed using MRI with a Siemens 3T Magnetom Vida scanner.

Secondary outcomes

The secondary outcomes are:

SPECIFIC FAT DEPOTS:

2. Change in hepatic fat content (baseline and 12-month follow-up). The quantification of hepatic fat content will be performed using MRI with a Siemens 3T Magnetom Vida

scanner.

3. Change in abdominal visceral adipose tissue (baseline, 12 weeks, and 12-month follow-up). The quantification of visceral adipose tissue will be assessed using MRI with a Siemens 3T Magnetom Vida scanner.
4. Change in abdominal subcutaneous adipose tissue (baseline, 12 weeks, and 12-month follow-up). The quantification of abdominal subcutaneous adipose tissue will be assessed using MRI with a Siemens 3T Magnetom Vida scanner.
5. Change in abdominal intermuscular fat content (baseline, 12 weeks, and 12-month follow-up). The quantification of intermuscular fat content will be assessed using MRI with a Siemens 3T Magnetom Vida scanner.
6. Change in pancreatic fat content (baseline, 12 weeks, and 12-month follow-up). The quantification of pancreatic fat content will be assessed using MRI with a Siemens 3T Magnetom Vida scanner.
7. Change in abdominal skeletal muscle tissue (baseline, 12 weeks, and 12-month follow-up). The quantification of skeletal muscle tissue will be assessed using MRI with a Siemens 3T Magnetom Vida scanner.
8. Change in mid-thigh subcutaneous adipose tissue (baseline, 12 weeks, and 12-month follow-up). The quantification of abdominal subcutaneous adipose tissue will be assessed using MRI with a Siemens 3T Magnetom Vida scanner.
9. Change in mid-thigh intermuscular fat content (baseline, 12 weeks, and 12-month follow-up). The quantification of intermuscular fat content will be assessed using MRI with a Siemens 3T Magnetom Vida scanner.
10. Change in mid-thigh intramuscular fat content (baseline, 12 weeks, and 12-month follow-up). The quantification of intramuscular fat content will be assessed using MRI with a Siemens 3T Magnetom Vida scanner.
11. Change in mid-thigh skeletal muscle tissue (baseline, 12 weeks, and 12-month follow-up). The quantification of skeletal muscle tissue will be assessed using MRI with a Siemens 3T Magnetom Vida scanner.

ELASTOGRAPHY:

12. Change in liver stiffness (baseline, 12 weeks, and 12-month follow-up). The quantification of liver stiffness will be assessed using shear wave elastography with a Canon Aplio i800.
13. Change in liver steatosis (baseline, 12 weeks, and 12-month follow-up). The quantification of liver steatosis will be assessed using attenuation imaging coefficient with a Canon Aplio i800.
14. Change in liver viscosity (baseline, 12 weeks, and 12-month follow-up). The quantification of liver viscosity will be assessed using shear wave dispersion with a Canon Aplio i800.

ANTHROPOMETRY AND BODY COMPOSITION:

15. Change in body weight (baseline, 6 weeks, 12 weeks, and 12-month follow-up). Body weight will be measured by a digital scale.
16. Change in waist circumference (baseline, 6 weeks, 12 weeks, and 12-month follow-up). Waist circumference will be assessed by measuring tape following the procedures outlined by the

International Society for the Advancement of Kinanthropometry.

17. Change in hip circumference (baseline, 6 weeks, 12 weeks, and 12-month follow-up). Hip circumference will be assessed by measuring tape following the procedures outlined by the International Society for the Advancement of Kinanthropometry.
18. Change in neck circumference (baseline, 6 weeks, 12 weeks, and 12-month follow-up). Neck circumference will be assessed by measuring tape following the procedures outlined by the International Society for the Advancement of Kinanthropometry.
19. Change in calf girth (baseline, 6 weeks, 12 weeks, and 12-month follow-up). Calf girth will be assessed by measuring tape following the procedures outlined by the International Society for the Advancement of Kinanthropometry.
20. Change in fat mass (baseline, 6 weeks, 12 weeks, and 12-month follow-up). Fat mass will be assessed by bioelectrical impedance analysis (BIA).
21. Change in fat-free mass (baseline, 6 weeks, 12 weeks, and 12-month follow-up). Fat-free mass will be assessed by BIA.
22. Change in bone mineral density and content (baseline, 6 weeks, 12 weeks, and 12-month follow-up). Bone mineral density and content will be assessed by dual-energy X-ray Absorptiometry (DXA).

BLOOD PRESSURE:

23. Change in systolic blood pressure (baseline, 6 weeks, 12 weeks, and 12-month follow-up). Systolic blood pressure will be assessed by blood pressure monitor.
24. Change in diastolic blood pressure (baseline, 6 weeks, 12 weeks, and 12-month follow-up). Diastolic blood pressure will be assessed by blood pressure monitor.

LIVER ENZYMES:

25. Change in levels of alkaline phosphatase (baseline, 12 weeks, and 12-month follow-up). Fasting blood samples will be used to asses alkaline phosphatase.
26. Change in levels of alanine transaminase (baseline, 12 weeks, and 12-month follow-up). Fasting blood samples will be used to asses alanine transaminase.
27. Change in levels of aspartate aminotransferase (baseline, 12 weeks, and 12-month follow-up). Fasting blood samples will be used to asses aspartate aminotransferase.
28. Change in levels of gamma-glutamyl transferase (baseline, 12 weeks, and 12-month follow-up). Fasting blood samples will be used to assess gamma-glutamyl transferase.

GLUCOSE HOMEOSTASIS:

29. Change in levels of fasting glucose (baseline, 12 weeks, and 12-month follow-up). Fasting blood samples will be used to assess fasting glucose.
30. Change in levels of HbA1c (baseline, 12 weeks, and 12-month follow-up). Fasting blood samples will be used to assess HbA1c.
31. Change in levels of fasting insulin (baseline, 12 weeks, and 12-month follow-up). Fasting blood samples will be used to assess insulin.

32. Change in levels of HOMA-IR (baseline, 12 weeks, and 12-month follow-up). Fasting blood samples will be used to assess glucose and insulin and HOMA-IR will be computed.
33. Change in 2-hour plasma glucose (baseline and 12 weeks). 2-hour plasma glucose will be assessed by an oral glucose tolerance test.
34. Change in levels of mean glucose (baseline and the last 2 weeks of intervention). 24-hour, diurnal and nocturnal mean glucose over 14 days will be assessed by continuous glucose monitoring during 2 weeks.

BLOOD LIPID PROFILE:

35. Change in levels of fasting triglycerides (baseline, 12 weeks, and 12-month follow-up). Fasting blood samples will be used to assess levels of triglycerides.
36. Change in levels of fasting high-density lipoprotein cholesterol (baseline, 12 weeks, and 12-month follow-up). Fasting blood samples will be used to assess levels of high-density lipoprotein cholesterol.
37. Change in levels of fasting low-density lipoprotein cholesterol (baseline, 12 weeks, and 12-month follow-up). Fasting blood samples will be used to assess levels of low-density lipoprotein cholesterol.
38. Change in levels of fasting total cholesterol (baseline, 12 weeks, and 12-month follow-up). Fasting blood samples will be used to assess levels of total cholesterol.
39. Change in levels of apolipoprotein A1 (baseline, 12 weeks, and 12-month follow-up). Fasting blood samples will be used to assess levels of apolipoprotein A1.
40. Change in levels of apolipoprotein B (baseline, 12 weeks, and 12-month follow-up). Fasting blood samples will be used to assess levels of apolipoprotein B.

CIRCULATING INFLAMMATORY BIOMARKERS:

41. Change in levels of C-reactive protein (baseline, 12 weeks, and 12-month follow-up). Fasting blood samples will be used to assess levels of C-reactive protein.
42. Change in levels of interleukin 6 (baseline, 12 weeks, and 12-month follow-up). Fasting blood samples will be used to assess levels of interleukin 6.

AMINO ACIDS:

43. Change in levels of essential amino acids (baseline and 12 weeks). Fasting urine samples will be used to assess levels of essential amino acids.
44. Change in levels of non-essential amino acids (baseline and 12 weeks). Fasting urine samples will be used to assess levels of non-essential amino acids.

DIETARY HABITS AND EATING BEHAVIOUR:

45. Change in energy intake (baseline, 6 weeks and 12 weeks). Energy intake (kcal/day) will be assessed by 24h recalls.
46. Change in carbohydrate intake (baseline, 6 weeks and 12 weeks). Carbohydrates intake (g/day and percentage of energy intake) will be assessed by 24h recalls.

47. Change in fat intake (baseline, 6 weeks and 12 weeks). Fat intake (g/day and percentage of energy intake) will be assessed by 24h recalls.
48. Change in protein intake (baseline, 6 weeks and 12 weeks). Protein intake (g/day and percentage of energy intake) will be assessed by 24h recalls.
49. Change in fiber intake (baseline, 6 weeks and 12 weeks). Fiber intake (g/day and percentage of energy intake) will be assessed by 24h recalls.
50. Change in dietary habits (baseline and 12 weeks). Dietary habits will be assessed by food frequency questionnaire (FFQ). Minimum value is 1 (never) and maximum value is 9 (more than 6 times per day). Higher values mean a higher frequency of a certain food consumption.
51. Change in appetite traits (baseline and 12 weeks). Appetite traits will be assessed by the Adult Eating Behavior Questionnaire (AEBQ). Minimum value is 1 (completely disagree) and maximum value is 5 (completely agree). Higher values mean a worse outcome.
52. Change in adherence to Mediterranean diet (baseline, 6 weeks, 12 weeks, and 12-month follow-up). Adherence to the Mediterranean dietary pattern will be assessed using validated questionnaires such as the PREDIMED questionnaire. The minimum value is 0 and the maximum value is 14. Higher values indicate better adherence to the Mediterranean diet and represent a better outcome.

SLEEP AND PHYSICAL ACTIVITY PATTERNS:

53. Change in Subjective sleep quality (baseline and 12 weeks). Subjective sleep quality will be assessed by the Pittsburgh Sleep Quality Index (PSQI). Minimum value is 0 (never) and maximum value is 3 (3 or more times per week). Higher values mean a worse outcome.
54. Change in objectively sleep quality (baseline and the last 2 weeks of intervention). Objectively sleep quality will be assessed by accelerometry.
55. Change in chronotype (baseline and 12 weeks). Chronotype will be assessed by the Munich Chronotype Questionnaire (MCTQ).
56. Change in morning-evening type (baseline and 12 weeks). Morning-Evening type will be assessed by the Morningness-Eveningness Questionnaire Self-Assessment Version. It defines if a person is more morningness or eveningness based on daily times preferences.
57. Change in moderate to vigorous physical activity levels (baseline, the last 2 weeks of intervention, and 12-month follow-up). Physical activity levels will be assessed by accelerometry.
58. Change in rest-activity rhythms (baseline and the last 2 weeks of intervention). Rest-activity rhythms will be assessed by accelerometry.
59. Change in step count (baseline and during the 12-week intervention). Step count will be assessed by activity band.

PSYCHOLOGICAL OUTCOMES AND QUALITY OF LIFE:

60. Change in depression traits (baseline and 12 weeks). Depression aspects will be assessed by the Beck Depression Inventory Fast Screen (BDI-FS). Values ranged from 0 to 63. Higher values mean worse outcome.
61. Change in stress traits (baseline and 12 weeks). Stress aspects will be assessed by the Perceived

Stress Scale (PSS). Values ranged from 0 to 40. Higher values mean worse outcome.

62. Change in anxiety traits (baseline and 12 weeks). Anxiety aspects will be assessed by the State-Trait Anxiety Inventory (STAI). Values ranged from 0 to 60. Higher values mean worse outcome.

5.2. Analysis methods

The main analyses will consist of the intention-to-treat analyses for the primary and secondary outcomes using a constrained baseline (meaning baseline-adjusted) linear mixed model, which accounts for baseline differences among the study groups. The model will include fixed effects

for time (three levels) and treatment (four levels) as well as the unique participant identifier as a random effect, and sex will be included as a covariate. Model assumptions will be checked. In case we detect model violations, we will take appropriate measures by e.g., conducting data transformations. If the global test of significance indicates between-group differences, pairwise comparisons will be explored. Although no adjustments for multiplicity will be performed, family-wise type 1 error rate on the primary outcome will be retained by using a hierarchical analytic approach. The prespecified hierarchical hypotheses will be tested using the prespecified sequence: TRE + Exercise versus UC, TRE versus UC, Exercise versus UC, TRE + Exercise versus TRE, TRE + Exercise versus Exercise, and TRE versus Exercise. The main statistical analyses will be performed by an independent researcher ([name]), who is not involved in the recruitment, evaluations, and interventions, and will be performed blinded to the treatment allocation by coding the intervention arms (e.g., A, B, C, D).

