4.3. Statistical analysis

The main analyses will consist of the intention-to-treat analyses for the primary and

Version: 2

secondary outcomes using a constrained baseline (meaning baseline adjusted) linear mixed model, which accounts for baseline differences among the study groups. The model will include fixed effects for time (three levels) and treatment (four levels) as well as the unique participant identifier as a random effect, and sex will be included as a covariate. Model assumptions will be checked. In case we detect model violations, we will take appropriated measures by e.g., conducting data transformations. If the global test of significance indicates between-group differences, pairwise comparisons will be explored. Although no adjustments for multiplicity will be performed, family-wise type 1 error rate on the primary outcome will be retained by using a hierarchical analytic approach. The prespecified hierarchical hypotheses will be tested using the prespecified sequence: TRE + Exercise versus UC, TRE versus UC, Exercise versus UC, TRE + Exercise versus TRE, TRE + Exercise versus Exercise and TRE versus Exercise. The main statistical analyses will be performed by an independent researcher ([name]), who is not involved in the recruitment, evaluations, and interventions, and will be performed blinded to the treatment allocation by coding the intervention arms (e.g., A, B, C, D).

It should also be noted that the intervention effect assessments will not only be based on statistical and practical significance (as usually done), but also on a practical benefit approach emphasizing and reporting unadjusted values that are intuitive to human judgment and readily replicable considering the design and methodology of this project.

5. Ethics and dissemination

The study has received ethical approval from the Granada Provincial Research Ethics Committee (CEI Granada - 0365-N-23) and will be performed following the ethical guidelines of the Declaration of Helsinki. Before their inclusion in the study, participants will be required to provide oral and written informed consent, with further details available in the Online Supporting Information.

Results will be presented in peer-reviewed, scientific journals and at international conferences. We aim to publish a main paper with the primary outcome data. Since it is a large study with numerous secondary outcomes, other specific manuscripts on each topic will be published.

6. References

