5.6. Statistical software

The analyses will be performed using R. For the main analyses we will use the ‘lme4’ or ‘LMMstar’ package. The use of packages will be reported in the manuscript.

6. References

1. Camacho-Cardenosa A, Clavero-Jimeno A, Martin-Olmedo JJ, et al. Time-restricted

eating and supervised exercise for improving hepatic steatosis and cardiometabolic health in adults with obesity: protocol for the TEMPUS randomised controlled trial. *BMJ Open*. 2024;14(1):e078472. doi:10.1136/bmjopen-2023-078472

7. Summary of changes to Statistical Analysis Plan

Date	Amendment
01/07/2024	Review and improvement of the statistical analysis methods, including constrained baseline (meaning baseline-adjusted) linear mixed model.
01/07/2024	Update of secondary outcomes including new outcomes derived from magnetic resonance imaging, elastography, fasting urine, and fasting blood samples.

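### The only covariance named for the three-visit model is a participant random effect, so 12-month data help set the standard error of the primary 12-week contrasts

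*SAP*

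**What the plan says.** The primary outcome in SAP 5.1 (version 2) is "Change in hepatic fat content (baseline and 12 weeks"); hepatic fat at 12 months is listed separately as a secondary outcome. Under SAP 2.7 the measurements "will be assessed at baseline, post intervention (12 weeks), and at a 12-month follow-up (12 months post intervention"). SAP 2.6 places the final analyses after all primary and secondary data have been collected, so the 12-month scans will be in the fit.

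SAP 5.2 says the main analysis is done "using a constrained baseline (meaning baseline-adjusted) linear mixed model". Its terms are fixed effects "for time (three levels) and treatment (four levels) as well as the unique participant identifier as a random effect", plus sex. Protocol 4.3 (version 2) has the same model: "fixed effects for time (three levels) and treatment (four levels) as well as the unique participant identifier as a random effect".

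Neither section states a residual covariance, visit-specific variances, a robust standard error or a degrees-of-freedom method, and neither writes a time-by-treatment term. On assumptions, SAP 5.2 says: "In case we detect model violations, we will take appropriate measures by e.g., conducting data transformations". On software, SAP 5.6 says: "For the main analyses we will use the ‘lme4’ or ‘LMMstar’ package", with no covariance setting.

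**The concern.** A participant random intercept with independent residuals implies compound symmetry: one variance at every visit and one correlation between every pair of visits. The 12-month visit falls a year after the intervention ends, and nothing in the documents supports the same variance or correlation there. If they differ, the pooled values misstate the variance of the 12-week contrast.

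The contrasts exposed are the 2.5-point differences in steps 2 to 5 of the testing sequence. Steps 4 and 5, TRE + Exercise against TRE and against Exercise, are comparisons that SAP 2.4 names for the main analyses. Because the sequence is fixed, lost power accumulates from step to step. In the other direction, a standard error that is too small would undermine the family-wise error control that SAP 5.2 claims for the primary outcome.

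**Working it through.** **Inputs from the documents (SAP 2.3, 3.1 and 5.2).** SD 6 points; correlation between baseline and 12 weeks 0.8; expected reductions 5, 2.5, 2.5 and 0, read as percentage points; two-sided alpha 0.05; 46 per arm with up to 20% dropout, so 46 × 0.8 = 36.8 completers per arm.

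**Assumptions.** The random effect is a random intercept with independent residuals. Treatment effects are visit-specific after baseline, as a constrained-baseline model implies. SDs at the other visits and correlations with the 12-month visit are not given, so they are varied.

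**The plan's own figure.** The stated minimum of 19 per group does not reproduce: f = 0.45 with 80% power needs 15 per group, and 19 gives 90.9%. That is a separate matter, and nothing below depends on it.

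**Formulas (complete data, n per arm).** Let v be the average of the three variances, c the average of the three covariances, and ρ = c/v. Write σ0 and σ1 for the SDs at baseline and 12 weeks, and r01 for their correlation.
- Reported SE² = (2/n) · v · (1 − ρ²)
- Actual SE² = (2/n) · (σ1² + ρ²σ0² − 2ρ·r01·σ0σ1)
- Unstructured SE² = (2/n) · σ1² · (1 − r01²)
- Type I error = 2[1 − Φ(1.96 × reported/actual)]

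**Worked case.** SDs 6/6/6, both 12-month correlations 0.7, n = 36.8:
- ρ = (0.8 + 0.7 + 0.7)/3 = 0.733
- reported SE = √[(2/36.8) × 36 × (1 − 0.538)] = 0.951
- actual SE = √[(2/36.8) × 36 × (1 + 0.538 − 2 × 0.733 × 0.8)] = 0.844
- ratio 1.126; type I error 2.7%
- unstructured SE = √[(2/36.8) × 36 × 0.36] = 0.839

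**Equal SDs of 6, r01 = 0.8, both 12-month correlations varied.** Power is for one 2.5-point contrast. The unstructured fit gives 85% at 36.8 per arm and 91.5% at 46.

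| 12-month r | Reported/actual SE | Type I error | Power, 36.8 per arm | Power, 46 per arm |
|---|---|---|---|---|
| 0.9 | 0.83 | 10.5% | 91% | 95% |
| 0.85 | 0.92 | 7.1% | 88% | 94% |
| 0.8 | 1.00 | 5.0% | 85% | 91.5% |
| 0.7 | 1.13 | 2.7% | 77% | 86.5% |
| 0.6 | 1.21 | 1.7% | 70% | 81% |
| 0.5 | 1.26 | 1.3% | 64% | 75% |
| 0.4 | 1.29 | 1.2% | 58% | 70% |

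Power at 0.85 and 0.9 is inflated by the understated SE. A 12-week global test then has type I error of 8.5% and 14.8%.

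**Unequal SDs (baseline/12 weeks/12 months), all correlations 0.8.**
- 6/7/6: ratio 0.90, type I error 7.7%
- 6/5/6: ratio 1.12, 2.8%
- 6/6/7: ratio 1.07, 3.5%
- 6/6/5: ratio 0.96, 5.9%

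**Offsetting cases.** SDs 6/7/6 with 12-month correlations 0.75, 0.7 and 0.6 give ratios 0.95, 0.99 and 1.05. SDs 6/7/8 with all correlations 0.8 give 1.02.

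**Sequence.** This is the chance of passing the global test and steps 1 to 5 in order, under the planned effects (400,000 draws, equal SDs). At 36.8 per arm it is 40%, 28%, 20% and 14% for 12-month correlations 0.7, 0.6, 0.5 and 0.4, against 55% unstructured. At 46 per arm it is 60%, 47%, 36% and 28%, against 72.5%. Global-test power stays at or above 98%, and the 5-point contrast keeps at least 99.8%.

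**Simulation check.** 4,000 REML random-intercept fits per scenario; 46 per arm, of whom 37 had all visits and 9 baseline only; missing completely at random; sex omitted.

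| Scenario | Mean reported SE | Empirical SD | Type I error |
|---|---|---|---|
| 6/6/6, all r 0.8 | 0.835 | 0.819 | 4.8% |
| 12-month r 0.9 | 0.695 | 0.827 | 10.1% |
| 12-month r 0.7 | 0.946 | 0.823 | 2.6% |
| 12-month r 0.6 | 1.038 | 0.844 | 1.5% |
| 12-month r 0.4 | 1.177 | 0.897 | 1.2% |
| 6/7/6, all r 0.8 | 0.896 | 0.980 | 7.5% |
| 6/5/6, all r 0.8 | 0.807 | 0.711 | 2.5% |

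In the same scenarios (2,000 fits each), an unstructured REML fit had type I error between 4.9% and 5.3%.

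**The case against.** The text is silent rather than explicitly wrong. It says random effect, not random intercept; it does not exclude another covariance; one of the two packages can fit one; and model assumptions will be checked. This is true, and the conclusion is conditional on the usual reading. But the only remedy named is transformation, so any other covariance would be chosen after the data are seen. SAP 5.2 also says the main analysis "will be performed blinded to the treatment allocation by coding the intervention arms". That limits choices favouring an arm but does not supply a covariance.

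The second reading may be generous to the plan. With no time-by-treatment term, a literal main-effects model would let 12-month data into the point estimate as well as its standard error. That is a further reason to write the terms out.

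The unequal-SD cases are not purely a 12-month effect. Compound symmetry on baseline and 12 weeks alone gives ratio 0.93 for SDs 6/7 and 1.10 for 6/5, against 0.90 and 1.12 with three visits. Roughly 70% and 85% of those errors come from forcing a common variance on the first two visits. The equal-SD table is the clean evidence for the role of the 12-month data.

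Direction is unknown. If correlation decays with time and SDs are equal, the tests are conservative and the cost is power. Milder decay costs less: with both 12-month correlations at 0.75, the SE is 7% too large and power is 81% against 85%. The inflated cases with equal SDs need 12-month correlations above 0.8, for which the documents give no support.

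Finally, the sample size was planned for a one-way ANOVA, which keeps its power in the equal-SD scenarios. Even the unstructured model passes steps 1 to 5 only 55% of the time with 20% dropout, so much of the weakness there comes from sample size and ordering. That stands, but the named covariance can lower the figure further.

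**Conclusion.** The concern holds. On the usual reading of the random effect, and with visit-specific treatment effects, the model gives a wrong 12-week standard error in general when variances or correlations differ between visits, unless the differences happen to cancel. With equal SDs the reported SE runs from 17% too small (12-month correlations 0.9, type I error 10.5%) to 29% too large (0.4, power 58% against 85%), and it is exact when all correlations are 0.8. These are scenarios; the documents do not show which applies. The consequence falls on the 2.5-point contrasts, while the global test and the first contrast keep high power in the equal-SD scenarios. The change should be made, though the conclusion carries medium confidence because it rests on two readings and on values that the plan does not give.

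**What to change.** In SAP 5.2 and Protocol 4.3:
- Write out the fixed effects: visit, arm-by-visit terms at each post-baseline visit with none at baseline, and sex.
- Replace the participant random effect with an unstructured within-participant covariance over the scheduled visits, fitted by REML with Satterthwaite degrees of freedom.
- Prespecify one fallback for non-convergence: compound symmetry with visit-specific variances, and cluster-robust standard errors by participant. In the simulated scenarios its type I error was 4.35% to 5.3%.

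In SAP 5.6, name LMMstar for the main analysis.

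The cost is wording in three sections. For hepatic fat the unstructured covariance has 6 parameters (the fallback has 4) against 2 for the random intercept. Four more is negligible with about 184 participants. No extra data or visits are needed.
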